4.3.2.6 Desensitisation (DS) Open Food Challenge (T3)

All participants who have completed at least 16 weeks of maintenance pancake OIT (Table 5 Step 7) will undergo an open cooked egg challenge at the end of treatment (T3) to assess for desensitisation. This is subjected to a total OIT duration (from initial escalation to exit challenge) of a minimum 12 months and maximum 18 months. All control subjects will undergo an open cooked egg challenge between 12 and 18 months (T3).

Desensitisation Open Food Challenge to Cooked Egg		
Dose	Egg Protein (mg)	Equivalent serving of cooked egg (g)
1	3	0.02
2	10	0.08
3	30	0.24
4	100	0.8
5	300	2.4
6	1000	8
7	3000	24
Cumulative dose		35.54

Table 7: Dosing protocol for DS Open FC to cooked egg

Successful desensitisation is defined as passing the FC to cooked egg, tolerating 4443mg of egg protein.

4.3.2.7 Sustained Unresponsiveness (SU) Food Challenge (T4)

Desensitised subjects in the active arm (tolerating 4443mg of cooked egg at T3) will be asked to stop OIT and all baked egg products (if they had been taking them) for approximately 6-8 weeks prior to returning for a repeat FC to assess for sustained unresponsiveness. The dosing protocol for SU FC will be the same as that of DS FC (Table 7).

Participants who tolerate 4443mg of cooked egg at SU FC will be allowed ad libitum cooked egg consumption post study. Participants who develop allergic reactions at SU FC will resume previous maintenance dose.

4.3.2.8 Clinical assessment and procedures during open FC (screening FC, baked egg FC, DS FC, SU FC)

All challenges will be conducted in the Allergy outpatient unit, with staff fully trained in the management of allergic reactions including anaphylaxis. Emergency equipment (including oxygen and suction) and medication will be checked beforehand, as per local protocol and international criteria for performance of FC.

All subjects will be assessed prior to FC to determine suitability for a challenge, as follows:

- No intercurrent illness
- No exacerbation in allergic symptoms (eczema, asthma, food allergy) in the preceding week.
- No short-acting β 2 agonists used in the past 12 hours
- No recent antihistamine exposure (e.g. cetirizine, loratadine) in the past 48 hours (72 hours for fexofenadine, 5 days for long-acting antihistamine (e.g. chlorphenamine, desloratadine).

- No oral steroids have been taken in the past 2 weeks
- Baseline observations (temperature, blood pressure, heart and respiratory rate, oxygen saturations,) within the normal range.
- Baseline physical examination must not reveal any significant acute findings.

The clinical team may elect to secure intravenous access by cannulation as an additional safety precaution at challenge. This will allow treatment to be easily and rapidly administered in the event of a significant allergic reaction, and also allows blood to be collected without further venepuncture.

Participants will be monitored including heart rate, blood pressure and oxygen saturations. Clinical manifestations will be assessed throughout the challenge.

Dose intervals should be between 20-30min but may be extended up to one hour at the investigator's discretion, where the participant may be experiencing an evolving reaction (as a safety measure, to limit the dose which might in turn moderate the symptoms experienced at challenge). A 2-hour observation period will follow the last dose to monitor for signs of reaction. For safety reasons, families will be asked to provide their child with a snack/ lunch to eat one hour after the last dose has been given or the challenge has been stopped due to reaction. Participants will then be observed for a second hour prior to leaving the unit.

Symptoms will be monitored during the challenge, with detailed assessment prior to each challenge dose, according to Figure 3.

- Green symptoms: Not generally sufficient to consider a challenge positive.
- Orange symptoms: Symptoms that recur on 3 doses or persist (e.g. 40 minutes) are more likely indicative of a reaction than when such symptoms are transient and not reproducible. 3 or more scoring areas in orange, more likely represent a true response.
- Red symptoms: A single red symptom is likely to indicate a true response, and if present the challenge should be halted.

The outcome of the challenge (positive or negative) and the apparent eliciting threshold dose will be recorded in the participant record. Challenge outcome will be determined as per the PRACTALL Consensus criteria, as shown in Figure 3; where possible, challenges should be stopped on the basis of at least one objective symptom.

Any allergic reaction occurring during in-hospital food challenge will be managed according to our unit's established protocol.

I. SKIN

A. Pruritus

- 0 = Absent
- 1 = Occasional scratching
- 2 = Scratching continuously for >2 minutes at a time
- 3 = Hard continuous scratching causing excoriations

B. Urticaria/Angioedema

- 0 = Absent
- 1 = < 3 hives, or mild lip oedema
- 2 = < 10 hives but >3, or significant lip, tongue or facial oedema
- 3 = Generalized involvement

C. Rash

- 0 = Absent
- 1 = Few areas of faint erythema
- 2 = Areas of erythema
- 3 = Generalized marked erythema (>50%)

II. UPPER RESPIRATORY

A. Sneezing/Itching

- 0 = Absent
- 1 = Rare bursts, occasional sniffing
- 2 = Bursts <10, intermittent rubbing of nose/eyes or frequent sniffing
- 3 = Continuous nasal/eye itch, periocular swelling and/or long bursts of sneezing, persistent rhinorrhoea

III. LOWER RESPIRATORY

A. Wheezing

- 0 = Absent
- 1 = Expiratory wheeze on auscultation
- 2 = Biphasic wheeze
- 3 = Use of accessory muscles, audible wheezing

B. Laryngeal

- 0 = Absent
- 1 = >3 discrete episodes of throat clearing/cough, or persistent throat tightness/pain
- 2 = Vocal hoarseness, frequent cough
- 3 = Stridor

IV. GASTROINTESTINAL

A. Subjective Complaints

- 0 = Absent
- 1 = Complaints of nausea or abdominal pain, itchy mouth/throat
- 2 = Frequent c/o nausea or pain with normal activity
- 3 = Notably distressed due to GI symptoms with decreased activity

B. Objective Complaints

- 0 = Absent
- 1 = 1 episode of emesis
- 2 = 2-3 episodes of emesis or diarrhoea or 1 of each
- 3 = >3 episodes of emesis or diarrhoea or 2 of each

V. CARDIOVASCULAR/NEUROLOGIC

- 0 = normal heart rate or BP for age/baseline
- 1 = Subjective symptoms (weak, dizzy), or tachycardia
- 2 = Drop in mean BP of >20% from baseline, or significant change in mental status.
- 3 = Cardiovascular collapse, signs of impaired circulation (unconscious)

Figure 3: PRACTALL consensus stopping criteria for food challenges

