4 STUDY DESIGN

This is a single site, open label interventional, randomised controlled trial evaluating the efficacy, safety and feasibility of pancake OIT, in inducing desensitisation and sustained unresponsiveness in egg allergic children between 2-15 years old. Participants will be recruited from the Allergy Department at KK Women's and Children's Hospital and assessed for eligibility based on the inclusion/ exclusion criteria listed. Those fulfilling criteria will be invited for an open FC to cooked egg (hard boiled), to confirm the diagnosis of an egg allergy (TS). *Children with a history of convincing clinical reaction to egg or failed a clinical egg food challenge within the last 6 months AND evidence of egg sensitisation on either skin prick test (SPT) or egg-specific IgE within the last 3 months will be exempted from this baseline FC. Those with a confirmed diagnosis of egg allergy will then be randomised 2:1 to active OIT or control.

Subjects randomised to the active arm will undergo a baked egg FC on a separate day in the unit (T0). This will be in the form of muffin baked by parents using standardised recipes (2 eggs in 6 muffins). *Children who have failed a baked egg FC within the last 6 months can be exempted from this baked egg FC. Depending on the outcome of the baked egg FC, they will be allocated to baked egg tolerant (BET) group (tolerating 2.5g baked egg) or baked egg reactive (BER) group (failing baked egg FC at any stage).

The BET group will undergo a 4-dose initial escalation with pancakes in hospital (37.5mg, 75mg, 150mg, 300mg egg protein) to determine the home starting dose of pancake (T1P). Those reacting at 37.5mg or 75mg will not begin OIT with pancakes but instead begin with cookies (Table 6 Step 11). The starting pancake dose will be administered at home daily for 4 weeks (minimum 3 weeks) before the next updosing to be performed in hospital. When

participants have successfully reached the target maintenance dose (Table 5 Step 7), they will remain on this maintenance dose for a minimum of 16 weeks (or total OIT duration of 18 months, whichever earlier).

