The BER group who tolerate at least 3mg of muffin in the baseline baked egg FC will undergo initial escalation with cookies in hospital (T1C). The first dose to be administered during the initial escalation will be individualised based on the outcomes of the baseline baked egg FC while the home starting dose will be the last dose tolerated during initial escalation. The starting cookie dose will be administered daily at home for a minimum of 2 weeks. Subsequent updosings will be done at home on a 2-weekly basis. When participants have successfully reached the target dose (Table 6 Step 11), they will remain on this dose for a minimum of 2 weeks before undergoing pancake initial escalation to begin pancake OIT (T2P). Those reacting at 37.5mg or 75mg will not begin OIT with pancakes but instead resume cookie OIT Step 11 for another minimum 4 weeks before re-attempting pancake initial escalation.

All participants who have completed at least 16 weeks of maintenance pancake OIT will undergo an open cooked egg FC at the end of treatment to assess for desensitisation (T3). Participants who tolerate 4443mg of cooked egg and deemed successfully desensitised will then stop OIT for approximately 6-8 weeks prior to returning for a repeat cooked egg FC to assess for sustained unresponsiveness (T4).

Participants who tolerate 4443mg of cooked egg at SU FC will be allowed ad libitum cooked egg consumption post study. Participants who develop allergic reactions at SU FC will resume previous maintenance dose.

Control subjects will receive the current best standard care, i.e. strict egg avoidance with provision of rescue medication and training. They will then undergo an open cooked egg FC between 12 and 18 months to assess for cooked egg tolerance.

Approximate time to complete study recruitment is 12 months. Total OIT duration from initial escalation to desensitisation FC is a minimum of 12 months and maximum of 18 months.

[figure not shown]

Figure 1: POET Study Design

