4.3.2.4 Cookie Initial Escalation (T1C) and Build-up Phase

The baked egg reactive (BER) group who tolerate at least 3mg of muffin will undergo initial escalation with cookies under medical supervision in the hospital on a separate day (T1C) to determine the home starting dose of cookie. This should be performed at soonest possible date after baked egg FC. The first dose to be administered during initial escalation will be individualised based on the outcome of the baseline baked egg FC. The NOAEL (No Observed Adverse Event Level) – defined as highest dose triggering none or transient Grade 1 symptoms) will be used for this purpose. Subsequent increments will be administered every 20-30 minutes and the maximum number of doses to be administered during the initial escalation is stipulated in Table 6 below. If a given dose triggers symptoms that causes discomfort to the participant or is deemed significant by the research team, no further doses will be administered on that day. Participants will be observed for at least one hour after dosing (2 hours if participant has previously experienced a delayed reaction). Participants will be instructed to have the last well-tolerated dose at home daily for a minimum of 2 weeks, until the next updosing is performed.

Subsequent updosings will be performed at home by the parents once every 2 weeks. The study team will conduct a phone call 2 weeks after the initial escalation and then monthly phone calls, to check on the progress of home updosing, ensure compliance and review any adverse events. When participants successfully reach the target dose (Step 11), they will remain on this dose for a minimum of 2 weeks before undergoing initial escalation with pancake (T2P). Subjects who react at 37.5mg or 75mg during pancake initial escalation will not continue with pancake OIT but instead resume cookie OIT Step 11 for a minimum of another 4 weeks before re-attempting pancake initial escalation.

Cookie Initial Escalation (IE) and Build-up Phase Protocol						
NOAEL at Baseline BE FC (mg)	STEP	Cookie Recipe	Cookie Amount	Egg Protein (mg)	Max Egg Protein at IE (mg)	Max no. of doses at IE
3	1	C	1	1.25	5	3
-	2	C	2	2.5	-	-
-	3	C	4	5	-	-
10	*3.5	D	0.5	6.25	37.5	3
30	4	D	1	12.5	75	3
-	5	D	3	37.5	-	-
100	6	E	1	75	150	2
300	7	E	2	150	300	2
-	8	E	4	300	-	-
1000	9	F	1	625	1250	2
-	10	F	2	1250	-	-
-	11	F	4	2500	-	-

Table 6: Cookie Initial Escalation and Build-up Phase Protocol

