9.2.1 Analysis of Primary Outcome

The primary analysis will compare the proportion of subjects who can tolerate 4443mg or more of egg protein in the active and control groups, using a two-sided Fisher's exact test.

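### Sections 4 and 4.3.2.7 state the threshold for stopping OIT and for free egg consumption as a weight of cooked egg, while sections 4.3.2.6, 9.2.1 and 9.2.2 state the pass mark in egg protein: an 8-fold difference on the protocol's own table

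*Combined protocol and SAP*

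**What the plan says.** Two sections give the decision thresholds as a weight of food:

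- Section 4, on leaving treatment after T3: "Participants who tolerate 4443mg of cooked egg and deemed successfully desensitised will then stop OIT". The same section uses 4443 mg of cooked egg again for unrestricted egg after T4.
- Section 4.3.2.7, on T3: "Desensitised subjects in the active arm (tolerating 4443mg of cooked egg at T3) will be asked to stop OIT". On T4: "Participants who tolerate 4443mg of cooked egg at SU FC will be allowed ad libitum cooked egg consumption post study".

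The definition and analysis sections give the same number as a weight of protein:

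- Section 4.3.2.6: "Successful desensitisation is defined as passing the FC to cooked egg, tolerating 4443mg of egg protein".
- Section 9.2.1, the primary outcome: "the proportion of subjects who can tolerate 4443mg or more of egg protein in the active and control groups".
- Section 9.2.2 sets the sustained unresponsiveness outcome at the same amount of egg protein.
- Section 3.3 sets the entry threshold at 4.443 g egg protein.

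Tables 2 and 7 carry egg protein (mg) and cooked egg (g) in separate columns, so the protocol treats them as different quantities.

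Similar wording occurs in the baked egg rules. Section 4 describes the "baked egg tolerant (BET) group (tolerating 2.5g baked egg", while section 6.1 says 2.5 g of egg protein. Section 4.3.2.4 refers to "The baked egg reactive (BER) group who tolerate at least 3mg of muffin", as do sections 1.2.4, 4 and 6.1 in similar words, while dose 1 of Table 3 is 3 mg of egg protein.

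**The concern.** The sentences in sections 4 and 4.3.2.7 decide which children stop OIT and go forward to T4, and which may then eat egg without limit. Such a threshold should have one meaning wherever it appears.

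The problem is sharpest at T4. Both operational statements of the T4 threshold are in cooked egg. The egg-protein version is found only in section 9.2.2, which staff running a challenge have little reason to open. At T3 the operational text is better anchored, because section 4.3.2.6 defines desensitisation in egg protein immediately before section 4.3.2.7.

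**Working it through.** **Inputs.** Seven challenge doses from Table 2, repeated in Table 7. Section 4.3.2.7 applies the Table 7 schedule to T4.

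**1. Reproduce the plan's totals.**
- Egg protein: 3 + 10 + 30 + 100 + 300 + 1000 + 3000 = 4443 mg.
- Cooked egg: 0.02 + 0.08 + 0.24 + 0.8 + 2.4 + 8 + 24 = 35.54 g.

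Both agree with Table 2. Nothing in the tables is miscalculated.

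**2. Conversion.** 35.54 g / 4.443 g = 8.0 g cooked egg per g protein, or 4443 / 35.54 = 125 mg protein per g cooked egg. Doses 2 to 7 each give 8.0. Dose 1 gives 6.7 because its weight is rounded to 0.02 g.

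**3. The threshold as literally written.** 4443 mg of cooked egg is 4.443 g, and 4.443 × 125 = about 555 mg protein. That is 555 / 4443 = 12.5%, or one eighth, of 4443 mg protein.

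**4. Position on the schedule.**

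| After dose | Cumulative protein (mg) | Cumulative cooked egg (g) |
|---|---|---|
| 5 | 443 | 3.54 |
| 6 | 1443 | 11.54 |
| 7 | 4443 | 35.54 |

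The literal 4.443 g (555 mg protein) falls between doses 5 and 6. It matches no step, but it has been exceeded once dose 6 is completed. As protein, 4443 mg is exactly the full seven-dose challenge.

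**5. Apply the T4 text to one child.** Suppose a child completes dose 6 and reacts to dose 7.
- On the literal cooked-egg wording the child has tolerated more than 4.443 g, so the sentence allowing free egg applies.
- The next sentence of section 4.3.2.7 sends any child who reacts at T4 back to the earlier maintenance dose, so it applies too.

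The two give opposite dispositions. On the egg-protein wording only the second applies.

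**6. The same child at T3.** Section 4 also requires that the child be deemed successfully desensitised, a term that section 4.3.2.6 defines in egg protein. The wording is inconsistent, but that definition limits its effect.

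**7. Baked egg wording.** Table 3 gives 1057 / 25.4 = 41.6 mg protein per g of muffin.
- If the 2.5 g in section 4 were read as muffin weight, it would hold 2.5 × 41.6 = 104 mg protein, against 2500 mg in the table, a 24-fold gap. Section 4 does not say muffin at that point, so this is only one possible reading.
- 3 mg of muffin would hold 0.003 × 41.6 = about 0.12 mg protein. The smallest portion in Table 3 is 3 mg protein, listed as 0.07 g of muffin, so no 3 mg portion of muffin is ever given.

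**The case against.** The best counter-argument is that no one following the tables would be misled. The figure 4443 is the protein total, T4 uses the Table 7 schedule, and the literal amount corresponds to no dose. Both analysed endpoints are expressly in egg protein. All of this stands. It makes a labelling slip the most plausible explanation and leaves the statistical endpoints untouched.

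A reader might infer that a child who reacts to the last dose simply passes and is released to unrestricted egg. The documents do not support that. Section 4.3.2.7 returns a child who reacts at T4 to the maintenance dose, and section 4 has the same rule. Section 4.3.2.8 has the challenge outcome recorded as positive or negative on PRACTALL criteria, so a qualifying reaction at dose 7 is a positive challenge. What remains is two conflicting instructions, not a rule that passes a reacting child.

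A reader might also infer that group allocation is at risk. This is not shown. Section 4 places any child who fails the baked egg challenge at any stage in the baked egg reactive group. Section 6.1 states that tolerant children will have taken 2.5 g of egg protein. The muffin wording cannot reclassify anyone when 3 mg protein is the lowest dose given, which is also the lowest NOAEL row in Table 6.

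The objection does not remove the contradiction in the operational sentences. That one reading is more plausible is an inference the reader has to make, and the T4 threshold in egg protein is not stated where the T4 decision is described.

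**Conclusion.** The inconsistency is real. Four sentences, two each in sections 4 and 4.3.2.7, state a decision threshold that is 8.0-fold lower than the pass mark in sections 4.3.2.6, 9.2.1 and 9.2.2 (about 555 mg against 4443 mg protein). The size rests only on Table 2's conversion. The practical consequence is confined to the operational text. At T4, a child who tolerates dose 6 and reacts to dose 7 meets two rules that conflict.

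The primary and sustained unresponsiveness endpoints, the sample size and the dosing tables are not affected. The baked egg and muffin phrases are consistency edits with no shown effect on allocation. Because the wording governs stopping treatment and unrestricted egg in allergic children, and costs almost nothing to correct, it should be corrected.

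**What to change.** Reconcile the four cooked-egg thresholds (T3 and T4, in sections 4 and 4.3.2.7) with sections 4.3.2.6, 9.2.1 and 9.2.2 and with Tables 2 and 7. State each on one basis, with the food weight in brackets. The sponsor should confirm which quantity is intended and put the T4 pass mark in section 4.3.2.7 itself. The sentence on free egg and the sentence on reactions at T4 should be checked together, so that every child falls under only one of them.

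In the same amendment, align the definition of baked egg tolerance in section 4 and the cookie entry wording in sections 1.2.4, 4, 4.3.2.4 and 6.1 with Table 3.

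This makes nine wording changes: four cooked-egg thresholds, one tolerance definition and four cookie entry statements. No extra participants, visits or procedures are needed, and the analysis does not change.

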4.3.2.3 Pancake Build-Up Phase

Each dose increment for pancake will be performed in the Allergy Unit under medical supervision, to confirm tolerance before the new dose is given at home daily for 4 weeks (minimum 3 weeks). Mild transient symptoms (e.g. itchy mouth) to the dose - transient (not lasting more than 20 minutes) Grade 1 symptoms (Table 8) - might be acceptable. If the updosing is not tolerated (i.e. more than mild transient symptoms), the participant will stay on the previously tolerated dose for another 4 weeks (minimum 3 weeks) before returning for repeat updosing.

Pancake Build-up Phase Protocol	Pancake Recipe A – 1 egg in 6 Pancake Recipe B – 2 eggs in 6			Min. no. of months on this step	Cumulative no. of months (minimum)
STEP	Pancake Recipe	Pancake amount	Egg Protein (mg)		
1	A	1/32	37.5	1	1
2	A	1/16	75	1	2
3	A	1/8	150	1	3
4	A	1/4	300	1	4
5	A	1/2	625	1	5
6	A	1	1250	1	6
7	B	1	2500	4	10

Table 5: Pancake Build-up Phase Protocol

When participants have successfully reached the target maintenance dose (Step 7), they will remain on this maintenance dose for a minimum of 16 weeks (or total OIT duration of 18 months, whichever earlier).

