4.3.2.10 Laboratory Assessments

The development of tolerance in immunotherapy is associated with several immunological changes, including decreases in egg-specific IgE levels with concomitant increases in IgG4 levels. Serum IgE to egg white, ovomucoid and ovalbumin will be performed at baseline screening (TS) and at the end of study (T3) for all subjects and additionally for active subjects who have a visit at T4.

Other than serum immunoglobins assay, 3 mL of Ethylenediaminetetraacetic acid anti-coagulated blood will be concurrently collected (TS, T3 and if applicable, T4) and sent to a core laboratory for peripheral blood mononuclear (PBMC) preparation. We expect 3 mL of blood to yield approximately 6 million PBMCs. These following experiments will be performed:

- i. DNA-human leukocyte antigen (HLA) genotypes: DNA will be isolated from 0.2 mL of blood to perform HLA typing to determine the appropriate candidates for major histocompatibility complex (MHC) tetramers analysis and genome sequencing if new data arises that indicates the importance of other non-HLA genetic variants for allergy manifestation.
- ii. Multi-parametric immune cell profiling: We will utilise multi-parametric cytometry to holistically characterise the immune system and determine the differences between non-responders and those with SU to identify immune signatures that confer resistance to OIT. Absolute counts of B, T, natural killer and dendritic cell subsets will be characterised.

- iii. Transcriptomic analysis: This will be done either at the immune cell subset or single cell level depending on the immune cell profiling data to identify the pathways responsible for the differences in response to OIT.
- iv. Multi-parametric cytokines/chemokines profiling: This will be done on the plasma stored after PBMC preparation if the cytometry data indicates the involvement of specific cytokines/chemokines in allergy manifestation.

4.3.3 Final Study Visit:

The final study visit will be on the day of DS challenge (T3) for controls and for active subjects who did not achieve desensitisation. The final study visit will be on the day of SU challenge (T4) for those successfully desensitised at T3.

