4.3.4 Post Study Follow up and Procedures

Subjects will be followed up by the Allergist in the clinical service and the monitoring and treatment of adverse events will be done during regular outpatient visits with the allergy team.

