6.3.2 In the event of omitted doses

- If 1-2 days of immunotherapy is missed, the subject can continue with the current dose at home with the next scheduled updose to proceed as planned
- If 3-7 days of immunotherapy are missed,

- for pancake build-up phase - the previous dose will be given until the subject can attend the Allergy unit for repeat updosing. *Upon resumption of original dose, subjects should be on the dose for at least 1 week before the next updosing.*
- for cookie build-up phase - the previous dose will be given for a week before repeat updosing at home. *Upon resumption of original dose, subjects should be on the dose for at least 1 week before the next updosing.*

• If more than 7 days of immunotherapy are missed, dosing should stop until the subject can attend the Allergy unit for repeat updosing of the previous dose.

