6.3.3 In the event of sick days

Families will be requested to contact the study team in the event of an intercurrent illness, to discuss reducing the dose depending on symptoms and intensity.

In the event of subject having an intercurrent illness, the investigator may pre-emptively reduce the OIT to the previous dose for the duration of the illness. *Upon resumption of original dose, subjects should be on the dose for at least 1 week before the next updosing.*

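### A child who reacts at the sustained-unresponsiveness challenge is told to resume the 2500 mg maintenance dose, whatever the eliciting dose or severity, with no supervised first dose stated

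*Combined protocol and SAP*

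**What the plan says.** Section 4.3.2.7 has children who passed the T3 challenge stop OIT and any baked egg for roughly 6-8 weeks before the repeat cooked egg challenge at T4. For a child who reacts there, the instruction is: "Participants who develop allergic reactions at SU FC will resume previous maintenance dose". Section 4 (Study Design) repeats it with no added condition.

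The protocol has only one maintenance dose, Step 7 of Table 5, which is 2500 mg of egg protein as pancake. Section 4.3.2.3 says: "When participants have successfully reached the target maintenance dose (Step 7), they will remain on this maintenance dose for a minimum of 16 weeks". Section 4.3.2.6 offers the T3 challenge to those who have completed that period, so a child who reaches T4 has been on 2500 mg.

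On challenges in general, Section 4.3.2.8 provides that "the apparent eliciting threshold dose will be recorded in the participant record". It also says "Any allergic reaction occurring during in-hospital food challenge will be managed according to" the unit's own established protocol, which is not among the documents.

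On what follows, Section 4.3.3 says "The final study visit will be on the day of SU challenge (T4) for those successfully desensitised at T3", and Section 4.3.4 says "Subjects will be followed up by the Allergist in the clinical service". Neither gives a procedure for restarting OIT.

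**The concern.** A child who passed 4443 mg of cooked egg at T3 and reacts at T4 has shown that tolerance of cooked egg has fallen during the break. The written rule then returns that child to the full dose in one step. Mild hives at 3000 mg and anaphylaxis at 30 mg lead to the same instruction. The eliciting dose is recorded, but nothing links it to the dose resumed.

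Elsewhere the protocol is more careful. After more than 7 missed days, Section 6.3.2 stops dosing until the child comes to the Allergy unit. After anaphylaxis at home, Section 6.3.1 has the next dose given under medical observation. Pancake increments are done in hospital (Section 6.3), and the home starting dose of pancake is set one step below the dose tolerated at initial escalation (Section 4.3.2.2). A child who reacts at T4 has had both a long gap and a fresh reaction, yet the T4 sentence states none of these safeguards.

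What is at stake is the safety of a small number of children. T4 is the last assessment, so no endpoint, comparison or power figure depends on this sentence.

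**Working it through.** **Inputs.** Challenge doses: 3, 10, 30, 100, 300, 1000 and 3000 mg (Table 7, which Section 4.3.2.7 also applies to T4). Resumed dose: 2500 mg (Table 5, Step 7). Break: 6-8 weeks (Section 4.3.2.7). Missed-dose limit: 7 days (Section 6.3.2).

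**The plan's own figure.** 3 + 10 + 30 + 100 + 300 + 1000 + 3000 = 4443 mg, which matches the stated cumulative dose.

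**Resumed dose against the amount eaten at T4.** The ratios are 2500 / single dose and 2500 / cumulative dose.

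| Reaction at dose | Single dose (mg) | Cumulative eaten (mg) | 2500 / single | 2500 / cumulative |
|---|---|---|---|---|
| 4 | 100 | 143 | 25 | 17.5 |
| 5 | 300 | 443 | 8.3 | 5.6 |
| 6 | 1000 | 1443 | 2.5 | 1.7 |
| 7 | 3000 | 4443 | 0.83 | 0.56 |

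At doses 1-3 the ratios are larger still. For any reaction at dose 6 or lower, 2500 mg is therefore more than everything eaten that day. For a dose-7 reaction it is below the eliciting dose, though still above the 1443 mg tolerated before it (2500 / 1443 = 1.7).

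**Length of the break.** 6 × 7 = 42 days and 8 × 7 = 56 days, which is 6 to 8 times the 7-day limit.

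**Children affected.** The documents do not give this number, so it rests on assumptions:

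- Active arm: 22 children.
- Desensitisation: 50-80%. Section 9.1 gives about 50% for baked egg and about 80% for raw or cooked egg, and assumes 65% for pancake.
- Sustained unresponsiveness (SU): 28-50% (Section 1.1, from other forms of egg). The text does not say whether the base is all treated children or only those desensitised, so both are used.
- Attrition: 0-30% (Section 9.1).

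Low end, SU as a share of all treated: 22 × 0.70 = 15.4 remain; 15.4 × 0.50 − 15.4 × 0.50 = 0.

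High end, SU as a share of those desensitised: 22 × 0.80 × (1 − 0.28) = 22 × 0.80 × 0.72 = 12.7.

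The range is about 0-13. With desensitisation held at the plan's 65%, it is about 2-10: 15.4 × 0.65 − 15.4 × 0.50 = 2.3 at the low end, and 22 × 0.65 × 0.72 = 10.3 at the high end.

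**The case against.** The strongest reply is that this is post-study care. T4 is the final study visit and an allergist then takes over. The sentence sits beside the permission for non-reactors to eat cooked egg freely, so it can be read as saying where the child goes next and not as a dosing procedure. It does not forbid supervision or clinical judgement. Active-arm families also already have an action plan, auto-injector training and round-the-clock access to the medical team (Section 4.3.2.5). All of that is true and limits the risk. It does not remove the point, because the protocol itself issues the instruction and attaches no condition to it.

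The dose ratios also overstate the contrast. The challenge uses cooked egg and maintenance is pancake, which Section 6.1 expects to be less allergenic. These children had earlier taken 2500 mg of pancake daily. No distribution of T4 thresholds is given, so the number reacting at dose 6 or lower is unknown and may be small. The ratios show the size of the step and do not predict how often children would react.

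Two stronger readings are tempting, and the documents support neither.

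- **That children take 2500 mg at home unsupervised.** No section says where the first resumed dose is taken. The defect is that no setting is stated.
- **That two rules conflict, 2500 mg here against a supervised 1250 mg under Section 6.3.2.** After more than 7 missed days that section says "dosing should stop until the subject can attend the Allergy unit for repeat updosing of the previous dose". Section 6.3.3 uses the same term for a step down: "the investigator may pre-emptively reduce the OIT to the previous dose for the duration of the illness". A reader might infer Step 6, 1250 mg. But Section 6.3.2 is written for missed doses and does not clearly cover a planned stop. The T4 sentence speaks of the maintenance dose, of which there is only one, and carrying the term over from the illness rule is inference. Sections 6.3.1 and 6.3.2 show how the protocol otherwise handles re-dosing. They do not establish a competing rule for T4.

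**Conclusion.** The point holds as a narrow safety gap. One rule covers every child who reacts at T4 after 42-56 days off treatment: resume 2500 mg of pancake, with no supervised first dose stated and no use of the recorded eliciting dose or of severity. Followed literally, a child who reacts at dose 6 or lower restarts above the whole amount of cooked egg eaten at that challenge. A child who reacts at dose 7 restarts below the eliciting dose.

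The comparison is an upper guide because the two foods differ. The count of about 0-13 of 22 rests on the assumed rates of desensitisation, SU and attrition, and not all of those children would react at dose 6 or lower. The omission itself is clear from the text. It is a cheap improvement and does not bear on the trial's validity.

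**What to change.** Replace the sentence in Sections 4 and 4.3.2.7 with:

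> Participants who react at the SU FC may resume OIT at a dose no higher than the previous maintenance dose, chosen by the investigator in light of the eliciting dose and severity at T4. The first resumed dose is given under supervision in the Allergy unit, and later updosing follows the existing rules (pancake in the unit, cookie at home).

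No fixed table from eliciting dose to restart step is proposed, because the documents give no basis for converting a cooked egg threshold into a pancake dose.

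**Cost.** Each affected child needs at least one extra unit visit, and Section 15 has families pay for consultations. A restart at pancake Step k needs 1 + (7 − k) visits and delays the return to maintenance by (7 − k) × 4 weeks:

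- Step 7: 1 visit, no delay.
- Step 6: 2 visits, 4 weeks.
- Step 5: 3 visits, 8 weeks.
- Step 1: 7 visits, 24 weeks.

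A cookie restart takes longer. For 0-13 children that is 0-13 visits in total if all restart at Step 7 and 0-26 if all restart at Step 6. Nothing changes in the endpoints, the analysis or the sample size.
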